3. INTERIM ANALYSIS

There are no formal interim analyses of clinical outcomes planned during the trial, hence no preplanned design changes or provisions to avoid an inflation of the Type I error.

As part of continuous monitoring, the DMC will be provided with confidential report by trial arm, containing information on recruitment, protocol compliance, safety data, interim assessments of outcomes (between-group estimates of differences in efficacy and/or safety outcomes), and conditional power for futility assessment if necessary. The DMC will inform the TSC if, in its view, there is evidence or reason why the comparison within the platform should be modified or terminated prematurely, for example, if the conditional power at a given point is low. Under such circumstances where unblinded information on efficacy is necessary and randomisation of care homes is still ongoing, the impact on the Type I error will be properly taken into consideration. If the TSC and sponsor decide that the recommended changes be implemented, then this will be done via study protocol amendments.

4. GENERAL ANALYSIS CONSIDERATIONS

4.1. Framework

The overall objective of the platform trial is to test the superiority of each intervention to standard care.

4.2. Analysis sets

Outcome	Analysis set
Primary, secondary and safety outcomes – individual-level	Contemporaneously randomised care homes and their eligible residents analysed according to the group their care home was randomly allocated to regardless of adherence to trial allocation (Intention-to-treat [ITT] analysis population).
	Since not all residents will be eligible for all trial interventions, residents in homes allocated to standard care will only be included in a given comparison if they were eligible to be given the intervention of interest had their home been randomised to it (i.e. not taking the intervention of interest, or another drug in the same class, and did not have any contraindications to it).
	In the case where an outbreak based on a positive result from a lateral flow test is not confirmed with a PCR test, then the site remains in the trial in the ITT analysis population.
	Primary analysis will be for participants with complete outcome data collected (i.e., without imputation for missing data).
Care home level infection rate	All residents in contemporaneously randomised care homes including residents not consenting to PROTECT-CH included in the comparison.

Outcome	Analysis set		
Supplementary analyses (for	All residents with consent regardless of whether		
primary outcome and the	eligible/took part in treatment phase of trial, analysed according to the group their care home was randomly allocated.		
secondary outcome related to			
transmission (time to SARS-			
CoV2 infection))			

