9.4. Reporting procedure

9.4.1. Adverse events

Specified adverse events will be reported directly into the eCRF for all participants, including those randomised to receive standard care. The data monitoring committee will review reported adverse events across all arms of the trial on a regular basis to monitor for any safety signals. Care home staff will be trained to report any adverse events that meet the criteria for a SAE and which are not excluded from requiring reporting via the SAE reporting process outlined in section 9.4.2.

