9.4.2. Serious adverse events

SAEs will be entered into a trial SAE form within the eCRF by a member of care home staff or GP directly responsible for the care of the participant. The person completing the report will include sufficient details of the event to facilitate the assessment of relatedness by a member of the national team of medically qualified Principal Investigators. Should a participant's general practitioner become aware of an SAE during the reporting period, they may report the event via the same process. A Principal Investigator will review the information in the SAE report and will liaise with the reporting care home or GP to obtain further information where necessary.

On receipt of an SAE, seriousness and causality will be determined independently by the PI. An SAE judged by the PI to have a reasonable causal relationship with the trial treatment will be regarded as a SAR. The PI will also assess all SARs for expectedness against the Reference Safety Information for the IMP. If the serious event is unexpected (i.e. is not defined in the protocol as an expected event) it will be classified as an unexpected SAR (SUSAR). Expedited reporting for SUSARs will be carried out as detailed in section 9.5.2.

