6.2. Adherence

The number and proportion of residents who did not receive the treatment they were allocated to as intended will be reported. Details on the number of days (or doses) of treatment received will be reported for all trial treatments received where available. Cluster-level non-adherence, if any, will also be reported alongside the participant non-adherence.

Information will also be reported on receipt of relevant concomitant medications received as part of the resident's usual care during the treatment period (e.g. steroid inhalers and oral steroids).

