8. ANALYSIS OF SAFETY

8.1. Serious adverse events (SAEs)

Safety reporting in the trial will focus only on those events that could be related to the trial medication, are serious in nature (according to the SAE definition in the protocol) and are unexpected (either the event itself or in severity) according to the reference safety information (RSI) for the IMP. Further information regarding the RSI can be found in the appendix in the protocol for the relevant IMP.

Descriptive summaries for each treatment group will be presented to show:

- The number and percentage of residents with at least one SAE and the total number of SAEs.
- The number and percentage of residents with at least one SAR (serious adverse reaction, related to IMP not unexpected), the total number of SARs and number with each event (MedDRA preferred term)
- The number and percentage of residents with at least one SUSAR (Suspected Unexpected Serious Adverse Reaction), the total number of SUSARs and the number with each event

Serious adverse reactions (SARs) and suspected unexpected serious adverse reactions (SUSARs) will be listed by treatment group.

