8.2. Adverse events relevant to the intervention

Adverse events relevant to the intervention as specified in the relevant IMP-specific protocol appendix will be reported on the eCRF by asking care home staff if the resident has experienced the event. These adverse events will be presented descriptively by treatment group for each pairwise comparison.

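### SAP 4.2 puts safety outcomes on the ITT set and SAP 8 names no exposed denominator, so IMP-arm SAR and SUSAR percentages understate the rate among dosed residents by the unstated never-dosed share (minor)

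*SAP*

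**What the plan says.** SAP 4.2 has one row headed "Primary, secondary and safety outcomes – individual-level". Its set is "Contemporaneously randomised care homes and their eligible residents analysed according to the group their care home was randomly allocated to regardless of adherence". SAP 7 and Protocol 4.2 fix eligibility before randomisation: in every arm, residents who are contraindicated to an IMP or already taking it leave the comparisons involving that IMP.

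SAP 8.1 then reports by treatment group. It gives "The number and percentage of residents with at least one SAR", does the same for SUSARs, adds total counts, and says "Serious adverse reactions (SARs) and suspected unexpected serious adverse reactions (SUSARs) will be listed by treatment group". For targeted adverse events, SAP 8.2 says "These adverse events will be presented descriptively by treatment group for each pairwise comparison". Neither section names an exposed or as-treated set. The only wider set in SAP 4.2, all consented residents, is used for the primary outcome and time to infection alone (also SAP 7.5).

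The definition of a SAR is in Protocol 9.4.2: "An SAE judged by the PI to have a reasonable causal relationship with the trial treatment will be regarded as a SAR". Targeted events are collected differently (Protocol 9.4.1): "Specified adverse events will be reported directly into the eCRF for all participants, including those randomised to receive standard care". On uptake, SAP 6.2 says "The number and proportion of residents who did not receive the treatment they were allocated to as intended will be reported", and adds days or doses received where those data exist.

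**The concern.** ITT is the right basis for a randomised safety comparison. A SAR percentage has another use: it describes what the drug does in people who take it, and safety through serious adverse reactions is a stated secondary objective. On the ITT set, an eligible IMP-arm resident who never starts treatment adds to the denominator and cannot add to the numerator.

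Such residents are foreseeable. IMP is prescribed, dispensed and shipped only after the home is randomised (Protocol 7.1), it is not given in hospital (Protocol 8.4), and SAP 6.2 itself provides for non-adherence by whole homes.

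The reverse case also exists. Protocol 11.1.3 lists treatment of an ineligible resident as a violation. A resident recorded as ineligible before randomisation but dosed in error is outside the SAP 4.2 set, so a reaction in that resident would not enter the by-arm percentages.

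At stake is how the published percentages are read. A reader who takes them as reaction rates in treated residents would take a figure that is too low.

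**Working it through.** **Inputs from the documents.** 200 homes x 32 residents = 6,400 per comparison, randomised 1:1 (Protocol 13.1, SAP 2.1), so 3,200 residents and about 100 homes in the IMP arm. The documents state neither a never-dosed share nor a SAR rate, so there is no plan figure for this point to reproduce.

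**Assumptions.** SAR rate among dosed residents r = 2.0%; never-dosed share s = 2%, 5%, 10% or 20%.

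**SARs and SUSARs.** Reported % = r x (1 - s).

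| s | Dosed, of 3,200 | Expected residents with a SAR | Reported % | Loss (points) | Factor to recover r, 1/(1 - s) |
|---|---|---|---|---|---|
| 2% | 3,136 | 62.7 | 1.96 | 0.04 | 1.02 |
| 5% | 3,040 | 60.8 | 1.90 | 0.10 | 1.05 |
| 10% | 2,880 | 57.6 | 1.80 | 0.20 | 1.11 |
| 20% | 2,560 | 51.2 | 1.60 | 0.40 | 1.25 |

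The numerator does not depend on the choice of denominator; only the percentage does. Each average-sized home that never gives the IMP adds 32/3,200 = 1 percentage point to s.

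**Against sampling error.** The 95% half-width at 2.0% is 1.96 x sqrt(0.02 x 0.98/3,200) = 0.485 points, ignoring clustering. The loss equals this at s = 0.485/2.0 = about 24%. If the planned design effect of 5.25 applied to SARs (assumption), the half-width would be 0.485 x sqrt(5.25) = 1.11 points and the matching s would be 1.11/2.0, about 56%.

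**Targeted adverse events.** The formula above does not carry over, because undosed residents still have background events. With rate d if dosed and background rate b, reported % = d(1 - s) + b x s. With d = 10% and b = 8% (both assumed) and s = 10%, this is 9.0 + 0.8 = 9.8%, against the 9.0% that the SAR formula would give.

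**Can s be recovered from the planned tables?** Only roughly. The SAP 6.2 count covers everyone not treated as intended, so it mixes never-treated with partly treated residents, and dose details depend on availability.

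**The case against.** The strongest reply has four parts.

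- **Unseen sources.** SAP 9 says dummy tables are appended, and Protocol 9 leaves further safety requirements to the IMP appendices. Either could set another denominator. This stands as a limit on the point. It does not remove it, because SAP 4.2 states the ITT rule for safety rather than leaving it open; if a table departs from that rule, SAP 4.2 needs aligning.
- **Existing cover.** SAP 8.1 gives counts and listings as well as percentages, SAP 6.2 reports non-receipt, and the most predictable never-dosed group, the contraindicated, has already been removed. This stands in large part, and the trial team could rebuild the denominator from its own data. A reader of the tables could only approximate it.
- **Few dosed in error.** IMP is prescribed only for eligible residents (Protocol 7.1), and the PI rechecks exclusions after allocation (Protocol 14.7). Cases should be rare. They remain covered by SUSAR reporting (Protocol 9.5.2), DMC review (Protocol 9.6), violation summaries (SAP 6.4) and possibly the SAR and SUSAR listings, which SAP 8.1 does not confine to the ITT set.
- **No decision changes.** Safety is descriptive, and across the assumed range the loss stays below sampling error. This is why the point is minor.

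A reader might go further and infer that a safety signal could be hidden or the randomised comparison biased. The documents do not support that: oversight does not run on these percentages alone, and ITT is what protects the comparison.

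**Conclusion.** The point holds as a minor gap in reporting. If any eligible IMP-arm resident is never dosed, the SAR and SUSAR percentages understate the rate among dosed residents by exactly the never-dosed share, in relative terms. For an assumed 2.0% rate and s of 2% to 20%, the loss is 0.04 to 0.40 points. SAR counts within the ITT set, the randomised comparison and the primary inference are unaffected.

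The size is not settled. A reader might infer that s must be tiny because few residents would be admitted or die before a first dose. Protocol 1.1 points that way, with about two weeks per disease transition. Protocol 1.2.4, however, gives symptom onset to death an interquartile range of 0 to 28 days, and neither refusal nor non-delivery in a home can be sized from the documents. A large s is equally unsupported.

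Nor should the ITT display be read as all-cause safety. Protocol 9.2.1 exempts many common events from reporting, Protocol 9.3 opens the minimum SAE window at first IMP administration, and SAP 8.1 narrows safety reporting to possibly related, serious and unexpected events.

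**What to change.** Keep the ITT tables as the main randomised display of reportable SAEs and targeted adverse events, without calling it all-cause. Add to SAP 4.2 an exposed set: all consented residents who received at least one dose of the IMP, whatever their recorded eligibility. In SAP 8.1, tabulate SARs and SUSARs on that set for the IMP arm, flag residents treated while ineligible, and label the table as non-randomised.

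The cost is one definition and one extra descriptive table per comparison, built from dose, violation and reaction data that the SAP already plans to report. The downside is that the exposed set has no randomised comparator and must not be set against standard care. For example, Protocol 13.1 assumes 10% admission plus 15% death. If 2% of the arm were admitted or died before a first dose and so never started (assumption), the figure among dosed residents would be (0.25 - 0.02)/(1 - 0.02) = 23.5% instead of 25%, with no drug effect at all.

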4.3. Timing of primary analysis

The primary analysis for each intervention will be performed once all participants in the active and usual care groups have reached 60 days of follow-up (or appropriate time point as detailed in the IMP appendix) and have outcome data available from both the care home (via the trial database) and the central routine data repository.

The secondary analysis of the ordinal outcome at 4 months will be performed once all participants in the active and usual care groups have reached this time point after randomisation and have outcome data available (as described above).

4.4. Statistical software

Analyses will be performed using Stata version 16 or above or R version 3.6.2 or above as appropriate.

4.5. Procedures for missing data

Missing baseline data

Missing data for the baseline covariates in the primary analysis (cluster-level minimisation factors and selected individual-level characteristics) is expected to be very rare. However, any missing baseline data will be imputed using the mean score at each care home in order to be able to include these participants in the analysis. These simple imputation methods are superior to more complicated imputation methods when baseline variables are included in an adjusted analysis to improve the precision of the treatment effect [6].

Missing outcome data

Missing values for the components of the composite primary outcome is expected to be very minimal as data collection for primary outcome will be combined with linkage to routine clinical data. In addition, ascertainment of the primary outcome measure will be performed centrally using UK death, hospitalisation and COVID-19 registers. As a result, primary analysis will be based on complete cases with the assumption that missingness is independent of the outcome, given the covariates. No imputation is planned.

5. DESCRIPTION OF PARTICIPANT CHARACTERISTICS

5.1. Participant flow

A CONSORT diagram will be used to summarise the flow of care homes into the trial and the flow of residents within care homes over the course of the trial. The flow diagram will include the number of care homes assessed for eligibility and those randomised. For each treatment group, the numbers of care homes that were randomly assigned, as well as the number of care homes and residents within care homes that received allocated treatment and were analysed for primary outcome will be

presented. Post-randomisation discontinuations will be presented by treatment group and overall, plus reasons.

5.2. Baseline characteristics

Baseline characteristics for cluster and individual participant levels will be summarised both overall and by treatment groups using appropriate descriptive statistics for continuous (mean, standard deviation, median, lower & upper quartiles, minimum, maximum and number of observations) and categorical (frequency counts and percentages) characteristics to illustrate balance between the groups at baseline. Baseline summaries will be based on the principal comparisons (between each treatment group and the concurrent standard care group respectively).

Cluster-level characteristics will include:

- Minimisation variables
 - care home type (residential vs nursing vs nursing and residential dual registration)
 - prior COVID-19 in care home at any time (yes vs no)
 - size of care home Total number of residents in care home (small (<30 residents), medium (>30, <50 residents), large (>50 residents))
 - care home has capacity to give oxygen (yes vs no)
- Any residents in care home received vaccination against COVID-19
- Any staff in care home received vaccination against COVID-19
- Country
- Care home ownership
- Registered for clients with learning disabilities
- CQC rating (outstanding, good, requires improvement) or equivalent in devolved administrations.
- Time between positive test for COVID-19 in resident/member of staff and care home randomisation (For PEP only)

Individual resident level baseline demographic and clinical characteristics will include:

- Age
- Sex
- Ethnicity
- BMI (from height and weight)
- Advance directive for no hospitalisation
- Do Not Attempt Resuscitation order
- Smoking status
- Co-morbidities (diabetes, heart disease, chronic lung disease, severe liver disease, severe kidney impairment, dementia, stroke)
- Previous positive test for COVID-19
- Tested positive for COVID-19 at randomisation (For PEP only)
- Received vaccination for COVID-19
- Time in care home
- Electronic frailty index
- Type of consent

6. ASSESSMENT OF STUDY QUALITY

6.1. Randomisation

The unit of randomisation is the care home, and thus eligible consenting individual residents will follow the treatment pathway to which their care home is randomised. Dynamic randomisation will be employed using a minimisation algorithm to balance across important baseline characteristics including:

- Care home type (residential vs mixed nursing/residential vs. nursing)
- Prior COVID-19 in care home at any time (yes vs no)
- Size of Care Home Total number of residents in care home (small (<30 residents), medium (>30, <50 residents), large (>50 residents))
- Care home has capacity to give Oxygen (yes vs no)

A team of central PIs will use the remote, internet-based randomisation system to obtain the treatment allocation for each care home after confirmation of care home participation and eligibility checks for the residents.

For trials of PrEP the care home will be randomised once an IMP has been identified by the NIHR POG and the necessary processes have been implemented.

For trials of PEP the care home will be randomised once an IMP has been identified by the NIHR POG and the necessary processes have been implemented and a resident or staff member in the care home has tested positive for SARS-CoV-2.

The number of care homes randomised to each treatment group will be tabulated. The minimisation variables will be tabulated (for each separate pairwise comparison of active treatment with the standard care treatment arm), as part of the baseline characteristics. The unlikely event of a care home withdrawing from the study will be reported with the timing and reasons for withdrawal, if available.

6.2. Adherence

The number and proportion of residents who did not receive the treatment they were allocated to as intended will be reported. Details on the number of days (or doses) of treatment received will be reported for all trial treatments received where available. Cluster-level non-adherence, if any, will also be reported alongside the participant non-adherence.

Information will also be reported on receipt of relevant concomitant medications received as part of the resident's usual care during the treatment period (e.g. steroid inhalers and oral steroids).

6.3. Follow-up and discontinuations

All reasonable efforts will be taken to minimise loss to follow-up, which is expected to be minimal as data collection for primary and secondary outcomes using trial-specific eCRFs is combined with linkage to routine clinical data on study outcomes. In addition, ascertainment of the primary outcome measure will also be performed centrally using UK death, hospitalisation and COVID-19 registers.

The number and percentage of homes and participants with follow-up information at day 60 days after randomisation will be reported by treatment groups.

6.4. Protocol deviations

Non-compliance with allocated treatment will be reported as described in Section 6.2 (Adherence).

Protocol violations are defined in the protocol. Non-compliance with the protocol will be reported on a deviation form and assessed by the NCTU to determine if constitutes a violation. The number of participants with protocol violations will be summarised by treatment group along with the type of deviation. Protocol violations will also be listed.

7. ANALYSIS OF EFFECTIVENESS

The analysis and reporting of the trial will be in accordance with CONSORT guidelines for cluster[7] and adaptive[8] designs. Analyses will be based on pairwise comparisons between each treatment arm and the concurrent standard care arm (reference group). Primary comparative analyses will be based on intention-to-treat principle, with all care homes and residents (eligible for the intervention prior to randomisation) within these care homes analysed according to treatment to which the care home was randomised. All tests will be two-tailed with point estimates and 95% confidence intervals for the treatment effect presented. No formal adjustment for multiple significance testing will be applied [9]. Secondary outcomes will be considered supportive to the primary outcome.

